## 2. Protocol Synopsis

FAST Study A Study to Demonstrate the Value of Paresthesia-Free Fast-Acting Subperception (FAST) and other SCS therapies using WaveWriter™ Spinal Cord Stimulator Systems in the Treatment of Chronic Pain	
Primary Objective	To evaluate the effectiveness of FAST-SCS (fast-acting paresthesia-free therapy) and additional SCS therapy options in patients with chronic pain using Boston Scientific WaveWriter SCS Systems.
Secondary Objectives	To determine the impact of WaveWriter SCS System on global patient outcomes and objective metrics including quality of life, patient preference, fitness etc.
Indication(s) for Use	The WaveWriter Spinal Cord Stimulator (SCS) System is indicated as an aid in the management of chronic intractable pain of the trunk and/or limbs, including unilateral or bilateral pain associated with the following: failed back surgery syndrome, Complex Regional Pain Syndrome (CRPS) Types I and II, intractable low back pain and leg pain.
Commercial Device/System	BSC WaveWriter™ SCS Systems
Study Design	Prospective, multi-center, single-arm study with an adaptive design
[REDACTED]	[REDACTED]
Planned Number of Sites / Countries	Up to 15 sites in the United States.
Safety Parameters	Rates of occurrence of all device hardware, device stimulation and procedure related non-serious adverse events, all serious adverse events, and unanticipated adverse events through the end of the study.

**FAST Study**

**A Study to Demonstrate the Value of Paresthesia-Free Fast-Acting Subperception (FAST) and other SCS therapies using WaveWriter™ Spinal Cord Stimulator Systems in the Treatment of Chronic Pain**

Primary Endpoint	Proportion of subjects with 50% or greater reduction from Baseline Visit in average targeted* pain intensity at 3 months post-activation, with no increase in baseline average daily opioid medications used to treat pain.  *targeted pain is the area of pain intended to be treated by SCS
Secondary Endpoint	The following secondary endpoints will be analyzed. Assessments required for deriving each endpoint are denoted in parentheses. 

• [REDACTED]

■ [REDACTED]

■ [REDACTED]

■ [REDACTED]

■ [REDACTED]

• [REDACTED]

■ [REDACTED]

■ [REDACTED]

■ [REDACTED]

[REDACTED]	[REDACTED]

**FAST Study**

**A Study to Demonstrate the Value of Paresthesia-Free Fast-Acting Subperception (FAST) and other SCS therapies using WaveWriter™ Spinal Cord Stimulator Systems in the Treatment of Chronic Pain**

	

• [REDACTED]

■ [REDACTED]

■ [REDACTED]

■ [REDACTED]

■ [REDACTED]

■ [REDACTED]

■ [REDACTED]

■ [REDACTED]

■ [REDACTED]

■ [REDACTED]

■ [REDACTED]

■ [REDACTED]

■ [REDACTED]

■ [REDACTED]

■ [REDACTED]

■ [REDACTED]

■ [REDACTED]

--	--------------------------------------------------------------------------------------------------------------------------------------------------------------------------------------------------------------------------------------------------------------------------------------------------------------------------------------------------------------------------------------------------------------

**FAST Study**

**A Study to Demonstrate the Value of Paresthesia-Free Fast-Acting Subperception (FAST) and other SCS therapies using WaveWriter™ Spinal Cord Stimulator Systems in the Treatment of Chronic Pain**

	

• [REDACTED]

■ [REDACTED]

■ [REDACTED]

■ [REDACTED]

■ [REDACTED]

■ [REDACTED]

■ [REDACTED]

■ [REDACTED]

--	-----------------------------------------------------------------------------------------------------------------------------------------------------------------------------------------------------------------

Follow-up Schedule	
Study events occur at the following time points:
 

• Screening

• Opioid Medication Lock Visit (Up to 35 days following Informed Consent)

• Baseline Period (14 days)

• Baseline Visit (0 - 7 days post Baseline Period)

• Implant Procedures (up to 90 days post Baseline Visit)

• Healing Period (14 - 28 days)

• Activation Visit (Day 0)

• Programming Lock Visit (70 - 7 days post-activation Visit)

• 3 Month Visit (90 + 14 days post-activation Visit)

• 6-Month Visit (180 ± 30 days post-activation Visit)

• 9-Month Visit (270 ± 30 days post-activation Visit)

--------------------	----------------------------------------------------------------------------------------------------------------------------------------------------------------------------------------------------------------------------------------------------------------------------------------------------------------------------------------------------------------------------------------------------------------------------------------------------------------------------------------------------------------------------------------------------------------------------------------------------------------------------------------------------------------------------------------------------------------

**FAST Study**

**A Study to Demonstrate the Value of Paresthesia-Free Fast-Acting Subperception (FAST) and other SCS therapies using WaveWriter™ Spinal Cord Stimulator Systems in the Treatment of Chronic Pain**

- Year 1 Visit (365 ± 30 days post-activation Visit)
- Year 2 Visit (730 ± 30 days post-activation Visit)

	

• Year 1 Visit (365 ± 30 days post-activation Visit)

• Year 2 Visit (730 ± 30 days post-activation Visit)

[REDACTED]	[REDACTED]
[REDACTED]	[REDACTED]
Inclusion Criteria	
IC1. Chronic pain (predominantly neuropathic) of the trunk and/or limbs for at least 6 months with back pain greater or equal to leg pain.
 

■ [REDACTED]

■ [REDACTED]

■ [REDACTED]

■ [REDACTED]

■ [REDACTED]

■ [REDACTED]

■ [REDACTED]

■ [REDACTED]

■ [REDACTED]

**FAST Study**

**A Study to Demonstrate the Value of Paresthesia-Free Fast-Acting Subperception (FAST) and other SCS therapies using WaveWriter™ Spinal Cord Stimulator Systems in the Treatment of Chronic Pain**

	
[REDACTED]
 
IC11. 22 years of age or older when written informed consent is obtained
 
[REDACTED]
 
IC13. Able to independently read and complete all questionnaires and assessments provided in English
 
[REDACTED]
 
IC15. Subject signed a valid, IRB-approved informed consent form (ICF) provided in English

Exclusion Criteria
	
[REDACTED]
 
[REDACTED]
 
[REDACTED]
 
[REDACTED]
 
[REDACTED]
 
[REDACTED]
 
[REDACTED]
 
EC7. Any pain-related diagnosis or medical/psychological condition or external factors that, in the clinician's best judgment, might confound reporting of study outcomes (e.g. pelvic pain, anginal pain, chronic migraine, brain or spinal cord tumor, involved in litigation, workmen's compensation)
 
[REDACTED]
 
[REDACTED]

**FAST Study**

**A Study to Demonstrate the Value of Paresthesia-Free Fast-Acting Subperception (FAST) and other SCS therapies using WaveWriter™ Spinal Cord Stimulator Systems in the Treatment of Chronic Pain**

[REDACTED]

EC15. Significant cognitive impairment at Screening that, in the opinion of the Investigator, would reasonably be expected to impair the study candidate's ability to participate in the study

EC16. Participating (or intends to participate) in another drug or device clinical trial that may influence the data that will be collected for this study

[REDACTED]

EC18. A female who is breastfeeding

EC19. A female of childbearing potential planning to get pregnant during the course of the study or not using adequate contraception

[REDACTED]

[REDACTED]

[REDACTED]

[REDACTED]

### FAST Study

## A Study to Demonstrate the Value of Paresthesia-Free Fast-Acting Subperception (FAST) and other SCS therapies using WaveWriter™ Spinal Cord Stimulator Systems in the Treatment of Chronic Pain

### Statistical Methods

#### Primary Statistical Hypothesis

The primary statistical hypothesis in this study is that the proportion of subjects with 50% or greater reduction from Baseline Visit in average daily targeted pain intensity at 3 months is non-inferior to the Objective Performance Criteria (OPC) of 40%

$$H_0: \pi_{opc} - \pi_t \geq 0.20$$

$$H_1: \pi_{opc} - \pi_t < 0.20$$

Where  $\pi_t$  is the proportion of subjects with 50% or greater reduction from Baseline in average daily targeted pain intensity at 3 months post activation with no increase in baseline average daily pain medications using WaveWriter.

[REDACTED]	[REDACTED]
[REDACTED]	[REDACTED]
[REDACTED]	[REDACTED]
[REDACTED]	[REDACTED]

**FAST Study**

**A Study to Demonstrate the Value of Paresthesia-Free Fast-Acting Subperception (FAST) and other SCS therapies using WaveWriter™ Spinal Cord Stimulator Systems in the Treatment of Chronic Pain**

## 4. Introduction

### 4.1. *Chronic Intractable Pain*

Chronic intractable pain is often defined as pain persisting for at least 6 months which has not responded to conservative treatment(s). The pain may be due to current or past nerve injury and causes significant disability, reduced work productivity, reduced quality of life, and significant cost burden.

The complexity of chronic pain and the diverse population it affects have resulted in varying results between the various treatment approaches including medications, physical therapy, stimulation etc. Early treatments for chronic pain typically include over the counter and prescription medications. Later treatments like physical therapy and interventional pain procedures (e.g. intraspinal injections, vertebroplasty, pulsed radiofrequency (RF) are attempted, sometimes followed by chronic high dose opioids and back surgery, if indicated. If back surgery is unsuccessful in relieving the chronic pain, the patient can be labeled as having failed back surgery syndrome (FBSS). Spinal cord stimulation (SCS) is an option in well-selected patients with chronic low back and/or leg pain.

### 4.2. *Spinal Cord Stimulation*

SCS is effective for chronic intractable pain associated with a variety of conditions, including, but not limited to, FBSS ((Carter et al., 2004, Taylor et al., 2004), complex regional pain syndrome (Sears et al., 2011), and low back pain and leg pain (Cameron et al., 2004). Spinal cord stimulation (SCS) is a less invasive treatment option for FBSS but has generally been reserved for patients who have failed multiple, and indeed all possible, repeat operations. With SCS, an implanted pulse generator (IPG) delivers electrical current to electrode(s) implanted in the epidural space. This current stimulates nerves and can be programmed to direct stimulation to the nerves innervating the painful location, resulting in a reduction of the intensity of that pain (Kumar et al., 2006). Before an SCS system is implanted, a patient often undergoes a screening trial with an electrode that is connected to an external stimulator that the patient wears outside of the body. The results of the screening trial can predict the patient's outcome with an implanted system (Kumar et al., 2006).

In SCS pain relief is realized when the nerves that innervate the painful region(s) are electrically stimulated (North et al., 1990). To increase the chance of success, the electrode contacts are programmed based on the patient feedback to various combinations of contact polarities (anodes and cathodes), pulse rate (or frequency), pulse amplitude (or current), and pulse width.

Traditionally, Spinal Cord Stimulation (SCS) has relied on the understanding that to achieve pain relief, dorsal column stimulation-induced paresthesia has to be generated around the area of pain in order to successfully treat pain (North et al. 1991). However, recent studies indicate that effective pain relief may be obtained by employing stimulation without paresthesia (Van Buyten et al., 2012, De Ridder et al., 2010, Kapural et al 2015, North et al., 2019).

Traditional SCS therapy optimization typically requires face to face interaction with healthcare professionals and ongoing iterations of programming sessions based on patient reported outcomes. Wearable devices, digital solutions, and other recent technology advances allow for more frequent, comprehensive monitoring. Additionally, frequent interaction with patients, while at home or remote, presents an opportunity to provide a treatment approach tailored to each patient using digital solutions.

This study, in addition to patient reported outcomes, will collect objective metrics including quality of life, patient preference, fitness etc. to determine the impact of the WaveWriter Systems in patients with chronic pain.

## **5. Commercial Device Description (part of Standard of Care)**

The WaveWriter™ Spinal Cord Stimulator (SCS) Systems are indicated as an aid in the management of chronic intractable pain of the trunk and/or limbs, including unilateral or bilateral pain associated with the following: failed back surgery syndrome, Complex Regional Pain Syndrome (CRPS) Types I and II, intractable low back pain and leg pain.

The System includes an Implantable Pulse Generator (IPG), External Trial Stimulator (ETS), Remote Control (RC), External Charger, and Clinician's Programmer (CP) and a portfolio of lead options. All tight-spaced lead options are available with the exception of the Artisan paddle, which is not permitted for use in this study. The IPG is rechargeable and is recharged transcutaneously by a charging unit. The System is capable of providing multiple waveforms.

The WaveWriter™ SCS System is approved by the Food and Drug Administration (FDA) and will be used per approved Instructions for Use (IFU) in this study.

## **6. Study Objectives and Endpoints**

### **6.1. Primary Objective**

To evaluate the effectiveness of FAST-SCS (fast-acting paresthesia-free therapy) and additional SCS therapy options in patients with chronic pain using Boston Scientific WaveWriter SCS Systems.

### 6.3. Primary Endpoint

The primary endpoint is the proportion of subjects with 50% or greater reduction from the Baseline Visit in average targeted\* pain intensity at 3 months post-activation, with no increase in baseline average daily opioid medications used to treat pain.

\* targeted pain is the area of pain intended to be treated by SCS

[REDACTED]

[REDACTED]

- [REDACTED]
- [REDACTED]
- [REDACTED]
- [REDACTED]
- [REDACTED]
- [REDACTED]
- [REDACTED]
- [REDACTED]
- [REDACTED]
- [REDACTED]

[REDACTED]

[REDACTED]

- [REDACTED]
- [REDACTED]
- [REDACTED]
- [REDACTED]

- [REDACTED]
- | [REDACTED]
- | [REDACTED]
- | [REDACTED]
- | [REDACTED]
- | [REDACTED]
- | [REDACTED]
- | [REDACTED]
- | [REDACTED]
- | [REDACTED]
- | [REDACTED]
- | [REDACTED]
- | [REDACTED]
- | [REDACTED]
- | [REDACTED]
- | [REDACTED]
- | [REDACTED]
- | [REDACTED]
- | [REDACTED]
- | [REDACTED]
- | [REDACTED]
- | [REDACTED]
- | [REDACTED]
- | [REDACTED]

### 6.6. *Safety Parameters*

Safety parameters include the rates of occurrence of all device hardware, device stimulation and procedure related non-serious adverse events, all serious adverse events, and unanticipated adverse events through the end of the study.

## 7. Study Design

The post-market study is a prospective, multi-center, single-arm study with an adaptive design. All participants will receive a WaveWriter Spinal Cord Stimulator (SCS) system and followed per the study schedule as shown in study schematic Figure 7.1-1.

[REDACTED]

[REDACTED]

[REDACTED]

[REDACTED]

[REDACTED]

[REDACTED]

[REDACTED]

[REDACTED]

[REDACTED]

[REDACTED]

[REDACTED]

[REDACTED]

**8. Subject Selection**

[REDACTED]

[REDACTED]

**8.2. Inclusion Criteria**

Subjects who meet all of the following criteria (see Table 8.2-1) may be given consideration for inclusion in this clinical investigation, provided no exclusion criterion (see Table 8.3-1) is met.

**Table 8.2-1: Inclusion Criteria**

Clinical Inclusion Criteria	IC1.	Chronic pain (predominantly neuropathic) of the trunk and/or limbs for at least 6 months with back pain greater or equal to leg pain.
		[REDACTED]
		[REDACTED]
		[REDACTED]
		[REDACTED]
		[REDACTED]
		[REDACTED]
		[REDACTED]
		[REDACTED]
		[REDACTED]
	IC11. 22 years of age or older when written informed consent is obtained	
	[REDACTED]	
	IC13. Able to independently read and complete all questionnaires and assessments provided in English	
	[REDACTED]	
	IC15. Subject signed a valid, IRB-approved informed consent form (ICF) provided in English	

**8.3. Exclusion Criteria**

Subjects who meet any one of the following criteria cannot be included in this study or will be excluded from this clinical study. No vulnerable populations will be enrolled in this study.

Vulnerable subjects are individuals who are unable to fully understand all aspects of the investigation that are relevant to the decision to participate, or who could be manipulated or unduly influenced as a result of a compromised position, expectation of benefits or fear of retaliatory response.

**Table 8.3-1 Exclusion Criteria**

Clinical Exclusion Criteria	
[REDACTED]
 
[REDACTED]
 
[REDACTED]
 
[REDACTED]
 
[REDACTED]
 
[REDACTED]
 
[REDACTED]
 
[REDACTED]
 
EC7. Any pain-related diagnosis or medical/psychological condition or external factors that, in the clinician's best judgment, might confound reporting of study outcomes (e.g. pelvic pain, anginal pain, chronic migraine, brain or spinal cord tumor, involved in litigation, workmen's compensation)
 
[REDACTED]
 
[REDACTED]
 
[REDACTED]
 
[REDACTED]
 
[REDACTED]
 
[REDACTED]
 
[REDACTED]
 
[REDACTED]
 
[REDACTED]
 
[REDACTED]

-----------------------------	-----------------------------------------------------------------------------------------------------------------------------------------------------------------------------------------------------------------------------------------------------------------------------------------------------------------------------------------------------------------------------------------------------------------------------------------------------------------------------------------------------------------------------------------------------------------------------------------------------------------------------------------------------

	
EC15. Significant cognitive impairment at Screening that, in the opinion of the Investigator, would reasonably be expected to impair the study candidate's ability to participate in the study
 
EC16. Participating (or intends to participate) in another drug or device clinical trial that may influence the data that will be collected for this study
 
[REDACTED]
 
EC18. A female who is breastfeeding
 
EC19. A female of childbearing potential planning to get pregnant during the course of the study or not using adequate contraception
 
[REDACTED]
 
[REDACTED]
 
[REDACTED]
 
[REDACTED]
 
[REDACTED]

--	----------------------------------------------------------------------------------------------------------------------------------------------------------------------------------------------------------------------------------------------------------------------------------------------------------------------------------------------------------------------------------------------------------------------------------------------------------------------------------------------------------------------------------------------------------------------------------------------------------------------------------------------------------------------------

## 9. Subject Accountability

### 9.1. Point of Enrollment

A subject will be considered enrolled in the study when the Informed Consent Form (ICF) is signed. All enrolled and activated subjects will be included in the study analyses.

If device implantation is unsuccessful, the subject will be followed for 2 weeks post implantation attempt to assess for procedure related adverse events.

### 9.2. Withdrawal

All subjects enrolled in the clinical study (including those withdrawn from the clinical study) shall be accounted for and documented. If a subject withdraws from the clinical investigation, the reason(s) shall be reported. If such withdrawal is due to problems related to

device safety or performance, the investigator shall ask for the subject's permission to follow his/her status/condition outside of the clinical study.

While study withdrawal is discouraged, subjects may withdraw from the study at any time, with or without reason and without prejudice to further treatment. In all cases of withdrawal or discontinuation, the Investigator will make all reasonable efforts to determine the reason for the subject's withdrawal. Subjects may be discontinued from the study for the various reasons, such as:

- Withdrawal of consent
- A safety concern defined by the Principal Investigator and/or Boston Scientific Neuromodulation (e.g., adverse event)
- Study non-compliance
- Inadequate use of device that may impact study outcomes
- Subject did not meet inclusion criteria or met an exclusion criterion after signing informed consent
- Surgical intervention that affects the Implantable Pulse Generator (IPG) and/or leads
- Lost to follow-up
- Death of the subject

A subject is considered lost-to-follow-up after 3 unsuccessful contact attempts have been made to reach the subject (including those who relocate but cannot be transferred to another participating site). Staff at the participating site should make a good faith effort to contact the subject with three documented communication attempts, at least one of which must be in writing, sent via a traceable method to inform the subject that the device must be programmed per standard of care with commercially approved settings.

Data collected up to the point of subject withdrawal, lost to follow-up, or until subject deletes the mobile app and/or ends data transmission may be used for study analysis in accordance with applicable regulations.

Subjects can stop data transmission by deleting the mobile app from their phone.

Withdrawn subjects will be followed per the End of Study Action Plan as described below.

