### ***9.3. Subject Status and Classification***

Subjects who provide written informed consent but do not meet all of the study eligibility criteria will not be implanted or activated. These subjects will be deemed as "enrolled but not activated" and their reason for ineligibility will be documented.

Enrolled subjects who are not activated will not count towards the enrollment cap. Subjects who sign consent, meet all eligibility criteria, undergo permanent implant and are activated cannot be replaced.

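### Activated subjects can leave the study before the 3-Month Visit under Sections 9.2 and 10.15.1, and the visible text gives no source for their primary outcome

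*Combined protocol and SAP*

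**What the plan says.** Section 9.2 is permissive and its list is open: "Subjects may be discontinued from the study for the various reasons, such as". The reasons listed include "Study non-compliance", "Inadequate use of device that may impact study outcomes" and "Surgical intervention that affects the Implantable Pulse Generator (IPG) and/or leads". No time limit is attached, and the list is not confined to subjects who have yet to be activated.

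Section 10.15.1 is mandatory on one point. A subject who declines a recommended lead revision is withdrawn but remains in the ITT and safety analyses. A subject who accepts revision continues on the original schedule.

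On what follows an exit:

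- Section 9.5 says that participation ends at withdrawal, with standard-of-care follow-up afterwards. After an explant there are two weeks of follow-up, for related adverse events.
- Section 9.2 says that "Data collected up to the point of subject withdrawal, lost to follow-up" or the end of app transmission may be used for analysis.
- If the withdrawal is due to device safety or performance, the investigator asks permission to "follow his/her status/condition outside of the clinical study".

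On who is analysed, Section 9.1 includes enrolled and activated subjects, and Section 11.2.1 defines ITT as those who received the device and were activated. Section 9.3 adds: "Subjects who sign consent, meet all eligibility criteria, undergo permanent implant and are activated cannot be replaced". The primary endpoint (Section 6.3) is read at the visit that the synopsis schedules as "3 Month Visit (90 + 14 days post-activation Visit").

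**The concern.** The exit rules and the analysis set point in different directions. Someone activated on day 0 and discontinued on, say, day 60 is still in the ITT denominator. The visible text provides no occasion on which their 3-month pain and opioid use would be measured.

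The exits concerned are not obviously random. Using a device too little, or refusing revision of a lead that has migrated or malfunctioned, can have many causes, but a link with poor response is plausible. The protocol does not state such a link.

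In a single-arm study there is no control group whose losses could show whether these exits are informative. Once the outcome has not been collected, any scoring rule puts an assumption in place of an observation. What is at stake is how many primary outcomes have to be assumed and how far the conclusion rests on them.

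**Working it through.** **Step 1. Follow one subject through the visible rules.**

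| Question | Where | Answer |
|---|---|---|
| Can an activated subject exit before day 90 + 14? | 9.2, 10.15.1 | Yes: may (9.2), must after declining a lead revision (10.15.1) |
| Does study follow-up continue? | 9.5 | No, participation ends |
| Is there a 3-month pain and opioid assessment after exit? | 9.2, 9.5 | None visible; only permission-based contact outside the study, or two weeks for adverse events after explant |
| Is the subject still analysed? | 9.1, 10.15.1, 11.2.1 | Yes, in ITT |
| Can the subject be replaced? | 9.3 | No |

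**Step 2. Inputs for an illustration of size.** From Section 11.1.1.1: performance criterion 0.40 and margin 0.20, so the rate to beat is 0.40 − 0.20 = 0.20. The visible text gives no sample size, alpha or loss rate, so there is no figure of the plan's own to reproduce. Assumed: N = 50, 100 or 200; one-sided alpha 0.025; a single-look exact binomial test; loss w from 0 to 20%; true responder rate p of 40%, with 50% as a check. Only losses between activation and about day 104 count.

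**Step 3. Critical count.** c is the smallest count with P(X ≥ c | N, 0.20) ≤ 0.025. This gives c = 17, 29 and 52 for N = 50, 100 and 200.

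**Step 4. Type I error if leavers are scored as non-responders.** The scored rate cannot exceed the true rate, so the error is at most P(X ≥ c | N, 0.20) = 0.0144, 0.0200 and 0.0236. There is no inflation.

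**Step 5. Power under the same scoring, if leavers would have responded like stayers.** X ~ Bin(N, p(1 − w)). For p = 0.40 the scored rate is 0.40 × (1 − w):

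| Loss w | Scored rate | N = 50 | N = 100 | N = 200 |
|---|---|---|---|---|
| 0% | 0.400 | 0.84 | 0.99 | >0.999 |
| 2% | 0.392 | 0.81 | 0.99 | >0.999 |
| 5% | 0.380 | 0.76 | 0.98 | >0.999 |
| 10% | 0.360 | 0.67 | 0.94 | 0.999 |
| 20% | 0.320 | 0.43 | 0.77 | 0.97 |

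For p = 0.50, power at 0, 5, 10 and 20% loss is 0.99, 0.98, 0.96 and 0.84 for N = 50. For N = 100 it is at least 0.99 throughout.

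These drops are the most that collecting the outcomes could recover. If every leaver is truly a non-responder, the scoring is correct and no power is lost.

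**Step 6. Dependence on the missing subjects.** With N = 100 and L outcomes missing, the conclusion turns on them when observed responders lie between 29 − L and 28. That is 27–28 for L = 2, 24–28 for L = 5 and 19–28 for L = 10.

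**The case against.** Four objections carry weight.

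1. *Mechanism and cost do not coincide.* The reason for concern is that leavers may be poor responders, but the power loss in the working arises only if they are not. Under non-responder scoring, the suspected mechanism does no harm to the test. This stands, and it limits the size of the point.
2. *The illustration is not the study's test.* Section 7 calls the design adaptive, and the rules are redacted. A fixed-N, single-look calculation may not match the real critical counts or power. This stands; the figures show order of magnitude only. Nothing visible supports losses of 10–20% in about 104 days.
3. *The answer may be redacted.* The 3-Month Visit section (between 10.10 and 10.12), Section 11.2.3, the data collection table and the SAP detail are not visible. They may contain an exit assessment or a scoring rule. This stands against any claim that either is missing. It does not remove the visible rule that participation ends at withdrawal, and a scoring rule would not collect the data.
4. *Safeguards exist.* Section 9.2 discourages withdrawal, its list is permissive, and activated subjects stay in the analysis. This protects the denominator but does not supply the outcome.

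A reader might go further and infer that these subjects would be dropped, so that the responder rate and the type I error are inflated. The documents do not support that: Sections 9.1, 10.15.1 and 11.2.1 point to their being kept in the denominator. A reader might also see a flat contradiction between Section 9.2 on implant surgery and Section 10.15.1 on accepted revisions. One is an open permissive list and the other a specific rule that probably governs. The defect is only that Section 9.2 states no exception.

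**Conclusion.** The point holds in limited form and is minor to moderate. The visible rules remove activated subjects from follow-up before the primary time point, while keeping them in the primary analysis set without replacement. This rests on what Sections 9.2, 9.5 and 10.15.1 say, not on their silence. It is not a finding that the plan lacks a missing-data rule or an exit assessment.

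The gain from correcting it is fewer assumed primary outcomes in a single-arm study. At 2–5% loss the effect is small unless N is small or the result falls near the boundary, and at a true rate of 50% it is smaller still. Every figure depends on the assumed N, alpha, loss, true rate and single-look exact test.

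**What to change.** 1. State in Sections 9.2, 9.5 and 10.15.1 that, for activated subjects, under-use, non-compliance, a declined revision, surgery on the IPG or leads, or explant does not by itself end outcome collection before the 3-Month Visit. Collect the 3-month pain and opioid assessment from them where consent allows. This concerns outcome collection only and changes no rule on device use, revision or removal.
2. Confirm that the SAP keeps every activated subject in the primary denominator and says how a missing 3-month outcome is scored. Only if it has no rule, add one. Non-responder scoring with a tipping-point sensitivity analysis is a conservative choice among several.
3. Reconcile Sections 9.2 and 10.15.1 on whether IPG or lead surgery ends participation, for example by a cross-reference. Which rule applies is for the sponsor to decide.

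The cost is wording in three sections and a few extra assessments. If non-responder scoring has to be added, it can lower the reported rate and power when exits are unrelated to response; item 1 limits this by reducing the number of subjects scored.
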